4.2.5 Safety parameters (Parts A & B, and Part C)

Safety variables

All safety analyses will be performed on the safety analysis set.

Where more than one measurement was made at baseline, the last non-missing pre-dose value will be taken as the baseline measurement.

If the baseline measurement is missing then the last non-missing pre-dose value will be taken as baseline.

Treatment exposure

Treatment exposure data will be collected for patients in Parts B and C. For Part B the mean daily dose will be summarised. For Part C the duration of treatment exposure, dose interruptions and reductions, mean daily dose and adherence will be summarised and listed.

Adverse events

All AEs will be listed for each patient, and will be summarised for Parts A & B, and separately for Part C of the study. In addition, the following summary tables will be presented by treatment (food condition (Part A) and olaparib 300 mg bd (Part B)) and across all patients for Part A, and across all patients only for Part C.

- Summary of number (%) of patients who had at least one adverse event in any category (Any AE, any causally related AE, any AE of CTCAE grade 3 or higher, any causally related AE of CTCAE grade 3 or higher, any AE with outcome = death, any causally related AE with outcome=death, any SAE (including events with outcome = death), any causally related SAE (including events with outcome = death), any SAE causing discontinuation of IP, any causally related SAE causing discontinuation of IP, any AE leading to discontinuation of IP, any causally related

AE leading to discontinuation of IP, any other significant AE, any other causally related significant AE).

- In addition, a summary of number (%) of AEs in any category (episode level) will also be presented.
- Summary of number (%) of patients who had at least 1 AE by preferred term, arranged by system organ class.
- Summary of number (%) of patients who had at least 1 AE by system organ class and preferred term presented by maximum reported CTCAE grade.
- Summary of number (%) of patients who had at least 1 olaparib/other causally related AE by preferred term.
- Summary of number (%) of patients who died, summary of number (%) of patients with an AE with outcome = death. In addition, a listing of deaths, and a listing of key information for AEs with outcome = death will be presented .
- Summary of SAEs (episode level) by preferred term, arranged by system organ class.
- Summary of number (%) of patients with SAEs by preferred term, arranged by system organ class. In addition, a listing of key information for SAEs, and a listing of key information for SAEs with outcome other than death will be presented.
- Summary of number (%) of patients who had an AE leading to discontinuation of IP, by system organ class and preferred term. In addition, a listing of key information for AEs leading to discontinuation of IP will be presented.
- Summary of number (%) of patients with any other significant AE by category. In addition, a listing of key information for other significant adverse events will be presented.

Part C only:

- Summary of number (%) of patients with an AE leading to olaparib dose reduction / interruption, by system organ class and preferred term.

Clinical laboratory variables (haematology, clinical chemistry, coagulation, urinalysis)

Project-specific reference ranges will be applied.

All laboratory safety data, incorporating haematology, clinical chemistry, coagulation (aPTT and INR will be collected at baseline in Part A) and urinalysis data will be listed for each patient and summarised where appropriate. Haematology, clinical chemistry and coagulation values outside the standard reference ranges will be highlighted in the listings. Numerical

laboratory data (absolute and change from baseline (Screening)) will be summarised by treatment (fed (A), fasted (A), olaparib 300 mg bd (B)) using standard summary statistics (mean, standard deviation, minimum, median, maximum, and number of patients). The only exception to this rule is for Screening and Follow-up assessments which will be summarised by treatment sequence for Part A and across all patients for Parts A & B, and across all patients for Part C.

Shift tables summarising the change from baseline to maximum CTC grade and to maximum value will be presented for haematology and clinical chemistry in Parts A & B and Part C. For urinalysis a shift table comparing baseline to the maximum value will be presented for Parts A & B only.

Vital signs and oral temperature

For Parts A & B, pulse, systolic and diastolic BP, height, weight and oral temperature will be listed by patient and summarised by treatment and part (fed (A), fasted (A), olaparib 300 mg bd (B)) using standard summary statistics for the absolute value at each protocol time and the change from baseline (Screening) to all subsequent protocol assessments. The only exception to this rule is for Screening and Follow-up assessments which will be summarised by treatment sequence and across all patients.

For Part C assessments will be summarised across all patients by study day.

ECG and physical examination

ECG and physical examination details will be listed individually by patient for Parts A & B, and will be summarised by treatment and part (fed (A), fasted (A), olaparib 300 mg bd (B)).

Physical examinations conducted during Part C will not be captured on the eCRF, but new or aggravated physical findings implying deterioration compared with baseline will be reported as an AE.

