AUC	Area under plasma concentration-time curve from zero to infinity
AUC _{0-t}	Area under plasma concentration-time curve from zero to the last measurable time point
AUC _{0-τ}	Area under plasma concentration-time curve over the dosing interval, τ
bd	Twice daily (Latin: bis die)
BP	Blood pressure
C _{avg}	Average plasma drug concentration over the dosing interval
C _{ss,avg}	Average plasma drug concentration over the dosing interval at steady state
CI	Confidence interval
CL/F	Apparent plasma clearance following oral administration
CL _{ss} /F	Apparent plasma clearance following oral administration at steady state
C _{max}	Maximum plasma drug concentration
C _{ss,max}	Maximum plasma drug concentration at steady state
C _{ss,min}	Minimum plasma drug concentration at steady state
CRF	Case record form
CSR	Clinical Study Report
CTC	Common terminology criteria (derived from National Cancer Institute Common Terminology Criteria for Adverse Events (NCI CTCAE) Version 4)
CV	Coefficient of variation
dECG	Digital electrocardiogram
ECG	Electrocardiogram
FI	Fluctuation index
%GCV	Geometric %CV
IP	Investigational Product
LOQ	Limit of quantification
λ _z	Terminal rate constant
MedDRA	Medical Dictionary for Regulatory Activities
NC	Not calculable
NQ	Non quantifiable
PD	Pharmacodynamics
PK	Pharmacokinetics
PR	PR interval of ECG
QRS	QRS interval of ECG

Abbreviation or special term	Explanation
QT	QT interval of ECG
QTc	QT interval corrected for heart rate
QTcB	QT interval corrected for heart rate using Bazett's correction
QTcF	QT interval corrected for heart rate using Fridericia's correction
QTcI	QT interval corrected for heart rate using individual-specific correction
R&D	Research and Development
RR	RR interval of ECG
SAE	Serious adverse event
SD	Standard deviation
$t_{1/2}$	Terminal half-life
t_{max}	Time to reach maximum plasma concentration
$t_{ss,max}$	Time to reach maximum plasma concentration at steady state
$t_{ss,min}$	Time to reach minimum plasma concentration at steady state
V_z/F	Apparent volume of distribution

AMENDMENT HISTORY

Date	Brief description of change
6 May 2014	Update to Global Product Statistician signatory.
Edition Number 2.0	ECG categories updated in section 4.2.4 . Updated Table 2 to include steady state / multiple dose PK parameters. Updated list of abbreviations with steady state PK parameters.
8 May 2014	Updated date format on page 1.
Edition Number 2.1	Replaced '6 th May 2014' on signature pages with 'Date'.

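### The value-based shift table takes the maximum for every haematology and chemistry variable, so where harm is a fall it shows the least affected value; the CTC-grade shift covers this only in part

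*SAP*

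**What the plan says.** The governing sentence is in SAP section 4.2.5, under clinical laboratory variables: "Shift tables summarising the change from baseline to maximum CTC grade and to maximum value will be presented for haematology and clinical chemistry". Its scope is "haematology and clinical chemistry in Parts A & B and Part C". It sets two endpoints for each variable, the highest CTC grade and the highest value. Urinalysis gets a value-based table only: "For urinalysis a shift table comparing baseline to the maximum value will be presented for Parts A & B only".

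The SAP does not define maximum value further, and section 4.2.5 contains no shift to a minimum.

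Three other statements bear on how low values can appear:

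- **Listings:** "Haematology, clinical chemistry and coagulation values outside the standard reference ranges will be highlighted in the listings".
- **Descriptive statistics:** numerical laboratory data get "standard summary statistics (mean, standard deviation, minimum, median, maximum, and number of patients"), and are "summarised by treatment (fed (A), fasted (A), olaparib 300 mg bd (B")). Part C is named only in the exception for Screening and Follow-up assessments.
- **Grading:** the abbreviation list explains CTC as "Common terminology criteria (derived from National Cancer Institute Common Terminology Criteria for Adverse Events (NCI CTCAE) Version 4"). Section 4.2.5 treats a higher grade as worse, for example in "any AE of CTCAE grade 3 or higher".

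**The concern.** A shift table should set each patient's baseline against the most adverse value seen afterwards. Which extreme is adverse depends on the variable. For some it is a rise. For others, such as haemoglobin, neutrophils and platelets, it is a fall. The SAP fixes one extreme, the maximum, for all of them.

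Where harm is a fall, the table then reports the reading at which the patient looked best. A reader of the study report could see a row of patients staying in the normal category and take that as evidence of no fall, although the table could not show most falls. Section 1.2 gives additional safety data as one of the two purposes of Part C, so the direction of these tables has some weight there.

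**Working it through.** There is no figure to reproduce. The check is which post-baseline extreme each planned output uses, and whether a fall can be seen in it.

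**Inputs.** The shift endpoints, their scope, the highlighting rule and the summary statistics come from SAP section 4.2.5. The meaning of CTC comes from the abbreviation list, and the visit pattern in Part C from section 1.2.

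**Step 1: shift to maximum value.** Take a variable where low is harmful and a patient who is normal at baseline.

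| Post-baseline course | Maximum value | Shown as | Fall visible? |
|---|---|---|---|
| Normal, low, normal | Normal | Normal to normal | No |
| Normal, then low to the end | Normal | Normal to normal | No |
| Low at every assessment | Low | Normal to low | Yes |

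The fall shows only if every post-baseline value is low. One normal reading is enough to hide it, even when the patient later falls and stays low. More assessments give more chances for such a reading. Section 1.2 sets Part C visits weekly for 4 weeks and every 4 weeks after that. The SAP does not show how many of those visits include laboratory tests.

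**Step 2: shift to maximum CTC grade.** Grade rises with severity. Where a low value is what is graded, the highest grade comes from the deepest fall. On the ordinary meaning of CTC grading, the first two patients in the table are therefore captured here if the fall raised the grade.

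**Step 3: what both shift tables miss.** Two kinds of fall remain:

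- a fall in a graded variable that leaves the grade unchanged;
- a fall in a haematology or chemistry variable that has no CTC grade for low values.

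**Step 4: whether another output tabulates these.**

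- The minimum in the descriptive statistics is the lowest value across patients at a summary point. It is not each patient's lowest value and is not tied to that patient's baseline.
- Those descriptive statistics are specified for the two food conditions of Part A and for Part B. For Part C they are named only at Screening and Follow-up. For vital signs, by contrast, section 4.2.5 states explicitly that Part C is summarised by study day. A general remark that laboratory data are summarised where appropriate fixes no Part C table.
- The highlighted listings contain the out-of-range values, but a listing does not count patients.
- The adverse event tables show a fall only if it was reported as an event.

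**Result.** The two falls in Step 3 appear in no per-patient tabulation, except where the value stays low at every assessment. In Part C, the two shift tables are the only per-patient tabulation of on-treatment laboratory change that the SAP names.

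**The case against.** The strongest reply is that the sentence at issue already contains the remedy. It plans a shift to maximum CTC grade beside the shift to maximum value, in every part. For haemoglobin, neutrophils and platelets, a fall that matters clinically would ordinarily raise the grade and so appear in the companion table. Adverse events are also tabulated by maximum CTCAE grade, Part C adds a table of events leading to dose reduction or interruption, and every out-of-range haematology and chemistry value is highlighted in the listings. The SAP prints neither the laboratory panel nor the grade thresholds, so no ungraded variable of clinical importance can be named from it.

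Most of this stands, and it rules out three stronger readings.

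- A reader might infer that the shift tables show the best value instead of the harmful fall. That is true of the value-based table alone. It is not true of the pair, because the grade table carries graded falls.
- A reader might infer that laboratory safety reporting points the wrong way throughout Part C. The grade shift, the adverse event tables and the listings all apply in Part C, so the documents do not support this.
- A reader might infer that the grade shifts must be split by direction for variables graded both high and low. A single maximum grade does leave the direction unstated, but nothing in the SAP is wrong without the split. It is a choice of display.

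The reply does not rescue the value-based table itself. Read literally, it uses the uninformative extreme where harm is a fall, and no minimum is planned. The sponsor may have meant worst value, but the text does not say so, and a programmer following it would output the maximum.

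**Conclusion.** The point holds in a limited form. The value-based shift table uses the wrong extreme for haematology and chemistry variables where harm is a fall. What is lost is falls that do not change the CTC grade and falls in variables without one. The consequence is greatest in Part C, for the reason shown in Step 4.

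Severity is low. These are descriptive tables with no test and no decision rule attached, and neither the food-effect analysis nor the QT analysis depends on them. The number of patients affected cannot be estimated from the SAP.

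The conclusion rests on three assumptions:

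- maximum value means the numerically highest post-baseline value;
- the value-based table sorts values into low, normal and high against the project reference ranges, since the SAP does not state its categories;
- low haemoglobin, neutrophils and platelets carry rising CTC grades, which is the ordinary meaning of the grading and is not printed in the SAP.

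**What to change.** In section 4.2.5, for haematology and clinical chemistry in Parts A & B and Part C, replace the shift to maximum value with a shift to minimum and to maximum value. Keep the shift to maximum CTC grade as it is. The urinalysis sentence need not change for this point.

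The cost is one extra set of descriptive shift tables. With two laboratory domains and the two study reports that section 4.1 describes (Parts A & B, and Part C), that is 2 × 2 = 4 further table groups. They use data already held and the same program with the minimum in place of the maximum. No assessment is added, and no other analysis changes.

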5. INTERIM ANALYSES (NOT APPLICABLE)

6. CHANGES OF ANALYSIS FROM PROTOCOL

There are no changes to the planned analysis from the protocol.

8. APPENDIX (NOT APPLICABLE)
